9.2.2. Secondary

Evaluation of Anhedonia

Change from treatment baseline in SHAPS score during the treatment period will be analyzed with the same MMRM model as primary efficacy variable (MADRS) using both: eITT and fITT analysis sets. The JNJ-67953964 treatment group will be compared with placebo using the appropriate contrast in the MMRM model at the 6-week endpoint.

Descriptive statistics for actual values and changes from baseline for SHAPS total score at each time point of the double-blind treatment phase will be provided by treatment group using both: eITT and fITT analysis sets. Mean differences between the treatments with corresponding CIs will be reported.

The effect of JNJ-67953964 on depression symptoms across different baseline levels of anhedonia will be explored. Descriptive statistics for actual values and changes from baseline in MADRS Score within different anhedonia levels (no anhedonia, low level of anhedonia and high level of anhedonia; cutoff values will be provided in Statistical Analysis Plan) will be presented by treatment group using both: eITT and fITT analysis set.

Evaluation of Depression

Descriptive statistics for actual values and changes from baseline for CGI-S, SATE and SMDDS (total) scores at each time point of the double-blind treatment phase will be provided by treatment group using both: eITT and fITT analysis sets. In addition, for CGI-S, frequency tables will be provided by treatment and time-point.

Evaluation of Anxiety

Descriptive statistics for actual values and changes from baseline for SIGH-A total score as well as HAM-A₆ score at each time point of the double-blind treatment phase will be provided by treatment group using both: eITT and fITT analysis sets. Mean differences between the treatments with corresponding CIs will be reported.

9.2.3. Exploratory

Cognitive Functioning Analysis

The actual values of CPFQ and changes from baseline will be summarized at each scheduled time point by treatment. These analyses will be performed on both: eITT and fITT analysis sets.

9.3. Biomarker Analyses

Biomarker levels will be tabulated for each time point and summary statistics will be calculated. Post-treatment changes in biomarker levels will be assessed by treatment group. Analysis of variance (ANOVA) and t-test will be used to assess differences across groups and time points. Correlations between biomarker levels and clinical endpoints will be evaluated.

The additional exploratory biomarkers will be tabulated by treatment and summary statistics will be calculated. Post-treatment changes in exploratory biomarkers will be summarized by treatment group. Associations between baseline biomarker levels and clinical endpoints may be explored. Additional exploratory analyses may also be performed. Results of all exploratory analysis (including the genetic/epigenetic results) will be presented in a separate report.

All biomarker data obtained from this study may also be included in an ongoing cross-study analysis to investigate the relationship between depression severity, phenotypes, and biomarkers.

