3. OBJECTIVES

OBJECTIVES

Primary Objective

The primary objective of this study is to evaluate the efficacy of JNJ-67953964 compared to placebo when administered as adjunctive treatment in subjects with MDD partially responsive to SSRI/SNRI treatment in terms of reduction of symptoms of depression, as assessed by the change from baseline on the Montgomery Asberg Depression Rating Scale (MADRS) in non-responders during the placebo lead-in period.

Secondary Objectives

The secondary objectives of this study are:

- To evaluate the efficacy of JNJ-67953964 compared to placebo when administered as adjunctive treatment in subjects with MDD partially responsive to SSRI/SNRI treatment in terms of reduction of symptoms of depression, as assessed by the change from baseline on the Montgomery Asberg Depression Rating Scale (MADRS) in both responders and non-responders during the placebo lead-in period.
- To investigate the overall safety and tolerability of treatment with adjunctive JNJ-67953964 in subjects with MDD when used in combination with a SSRI or SNRI.
- To investigate the effect of JNJ-67953964 versus placebo on depression related anhedonia as assessed by the Snaith-Hamilton Pleasure Scale (SHAPS).
- To investigate the effect of JNJ-67953964 on symptoms of depression using the Clinical Global Impression-Severity (CGI-S), the patient reported Symptoms of Major Depressive Disorder Scale (SMDDS) and the self-assessment of treatment experience (SATE).
- To investigate the effect of JNJ-67953964 on symptoms of anxiety using the Hamilton Anxiety Scale (HAM-A) and on core symptoms of anxiety using the HAM-A₆ subscale.

- To assess the plasma PK of JNJ-67953964 in subjects with MDD and explore its relationship with efficacy and safety parameters.

Exploratory Objectives

- To explore the effect of JNJ-67953964 on aspects of cognitive and executive function using the Cognitive and Physical Functioning Questionnaire (CPFQ).
- To explore mood-related biomarkers (including but not limited to growth factors, hypothalamic–pituitary–adrenal [HPA] axis markers, immune system activation, metabolic markers) and genetic/epigenetic variation that may be related to clinical response, nonresponse, or safety and tolerability parameters of JNJ-67953964.

Hypothesis

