8. STUDY ASSESSMENTS AND PROCEDURES

8.1. Overview^a

The TES summarizes the frequency and timing of efficacy, PK, PD, biomarker, and safety measurements applicable to this study.

When possible, all PRO assessments should be conducted/completed before any tests, procedures, or other consultations to prevent influencing participant perceptions.

^a This section has been amended by amendment INT-1.

However, during the site visits, it should be considered that the study medication has to be taken in fasted condition and it is preferred to have the PRO's and other assessments done in fed condition. So, during the site visits it is recommended that procedures should be performed in the following sequence: Blood and urine collection (when in fasted condition), dosing, breakfast, PRO, interview with investigator (SIGMA, SIGH-A and C-SSRS), safety assessments. Blood collections for PK and PD assessments should be kept as close to the specified time as possible.

When a subject is expected to be impacted by blood draw, the sequence may be: PRO, blood and urine collection (when in fasted condition), dosing, breakfast, interview with investigator (SIGMA, SIGH-A and C-SSRS), safety assessments.

Additional serum (by central laboratory) or urine pregnancy tests may be performed, as determined necessary by the investigator or required by local regulation, to establish the absence of pregnancy at any time during the participation in the study.

The total blood volume to be collected from each participant will be approximately 217 mL.

Repeat or unscheduled samples may be taken for safety reasons or for technical issues with the samples.

For each participant, the maximum amount of blood drawn from each participant in this study will not exceed 300 mL.

Volume of Blood to be Collected from Each Participant

Type of Sample	Volume per Sample (mL)	No. of Samples per Participant	Approximate Total Volume of Blood (mL) ^[a]
Safety (including screening and post-treatment assessments)			
- Hematology	2	5	10
- Serum chemistry, HbA1c and gastric mucosa panel	6.5	5	32.5
Serology (HIV, hepatitis)	5	1	5
TSH/FT4	2.5	1	2.5
Serum β-hCG pregnancy tests, FSH	5	1	5
Pharmacokinetic samples	6	9	54
Biomarkers serum ^[b]	20	3	60
Biomarker plasma	10	3	30
Genotyping/(epi)genetics	6	3	18
Approximate Total ^[c]			217

a. Calculated as number of samples multiplied by amount of blood per sample.

b. Biomarker serum sample represents combined volume of more than one tube

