8.9. Biomarkers

During the study, blood and saliva will be collected for the assessment of biomarkers at the time points indicated in the TES. Additional instructions for collection of biomarker samples:

- Blood biomarkers will be collected under fasting conditions – at least 4 hours, water permitted.
- Subjects should be informed not to do strenuous sports or exercises within 24 hours before blood sample collection.
- Food, drinks (except water) and oral care (brushing, flossing, mouthwash) are not permitted for 1 hour prior to saliva collection.
- Subjects should refrain from alcohol consumption for 12 hours prior to saliva sampling.
- Subjects may receive a reminder via the smartphone to collect the saliva samples on time.

In blood and/or saliva, biomarkers related to the HPA axis activation including but not limited to ACTH and cortisol, neurotropic factors, inflammation and metabolic factors may be investigated.

Biomarkers may be added or deleted based on scientific information or technical innovations under the condition that the total volume of blood collected will not be increased. The biomarker data obtained from this study may also be included in an ongoing cross-study analysis to investigate the relationship between depression severity and phenotypes and biomarkers.

Subject data

To evaluate the biomarker results, the following information needs to be documented on each day of collection of blood samples for biomarker analysis.

- Diet (extremes during the previous week)
- In WOCBP: Follicular phase by documenting first day of last menses.
- Any sickness or allergy in the previous 2 weeks

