9. STATISTICAL CONSIDERATIONS

9.1. Sample Size Determination

The sample size for the study is determined based on the assumption of a treatment effect size of 0.45 in the mean change from baseline in MADRS total score between JNJ-67953964 treatment group and placebo. The assumed effect size is based on review of the literature looking at the adjunctive treatment with ALKS 5461, a combination of buprenorphine (partial m-opioid receptor agonist and KOR antagonist) and samidorphan (a potent m-opioid receptor antagonist) in MDD patients with an inadequate response to one or two courses of an antidepressant (Fava 2016 and Enrich 2015).

Using the data from the same studies, an estimate of 11 for standard deviation in the change in MADRS total score from baseline was made. Detection of 0.45 effect size with a power of 90% at an overall 1-sided significance level of 0.20, requires 45 subjects in each treatment group (90 subjects in total).

The choice of alpha and beta (1-power) for this Phase study was made in order to increase sensitivity for detecting a therapeutic signal while also maintaining a modest sample size. Thus, power was set to a high value (power=90%; beta=0.10) but the type 1 error rate was specified at 1-sided alpha=0.20. This choice is supported by a publication by Lindborg et al (Lindborg 2014) in which authors note that type 1 and 2 error levels commonly employed in Phase 3 study designs (simple hypothesis tests with 2-sided alpha=0.05 and beta=0.2) are suboptimal for early phase studies and that switching these values (increasing alpha while decreasing beta) can increase Phase 2 productivity and reduce the risk of rejecting a compound with significant therapeutic potential.

When adjusted for a drop-out rate of approximately 5% of subjects during the treatment period, the required number of subjects to be randomized is 96. To achieve this, the estimated number of subjects to enter the lead in period is 142, after adjusting for an estimated placebo response rate of 25% and drop-out rate of 10% during the lead-in period.

A blinded sample size re-estimation is anticipated with 180 as the maximal number of subjects to be enrolled in the trial.

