9.2. Efficacy Analyses

9.2.1. Primary

Primary efficacy analyses will be based on the intention-to-treat analysis set from enriched population (eITT) which consists of randomized lead-in placebo non-responders receiving at least one dose of study medication and having at least one post-treatment baseline efficacy measurement.

The JNJ-67953964 treatment group will be compared with placebo using the primary efficacy endpoint: change from treatment baseline in MADRS score during the treatment period. The comparison will be performed by means of a mixed-effects model for repeated measures

(MMRM), with time, treatment (placebo, JNJ-67953964) and time-by-treatment interaction as factors and baseline total MADRS score as a continuous covariate. Other covariates of interest may be included in the MMRM model. The treatment-placebo differences will be obtained using the appropriate contrast in the MMRM models at the 6-week endpoint.

Sensitivity analyses of the primary endpoint will be performed using an analysis of covariance (ANCOVA) model; these will be detailed further in the Statistical Analysis Plan.

In addition, same MMRM model will be fitted on full intention-to-treat analysis (fITT) set consisting of all the randomized subjects receiving at least one dose of study medication and having at least one post-treatment baseline efficacy measurement.

Missing data mechanisms exploration and possible imputation methods for primary efficacy variable will be described in detail in Statistical Analysis Plan.

Descriptive statistics for actual values and changes from baseline for MADRS Score at each time point of the double-blind treatment phase will be provided by treatment group using both: eITT and fITT analysis sets. Mean differences between the treatments with corresponding confidence intervals (CIs) will be reported.

Frequency tables for response and remission of depressive symptoms (derived from the MADRS) will be provided by treatment group at each time point of the double-blind treatment phase using both: eITT and fITT analysis sets. Chi square test to test the overall differences between the treatment groups will be performed.

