**Table 1: Overview of Trials to be Included in the Population PK Analysis**

Study No.	Study Title & Design	Brief Description of PK Data
67953964MDD2001	
Title: A Phase 2a Randomized, Double-blind, Placebo-Controlled, Parallel-Group, Multi-center Study Investigating the Efficacy, Safety, Tolerability and Pharmacokinetics of JNJ-67953964 in Subjects with Major Depressive Disorder.
 
Design: The treatment phase of the trial will consist of 3 periods. A placebo lead-in period of concealed duration, after which subjects will enter the double-blind treatment period when they will be randomly assigned to 10 mg JNJ-67953964 q.d. or continue placebo in a 1:1 ratio for 6 weeks. Subjects who complete the treatment period, will then enter the withdrawal period and be treated with placebo for the remaining time of the treatment phase of the study.
	
No. of subjects with PK data available/total no. in study: 71/142 (Planned)
 
PK samples are collected for plasma concentrations of JNJ-67953964 before and 2 hours after dosing on Day 22 (Day 1 Treatment Period), 29 (Trt Week 1), 43 (Trt Week 3) and 64 (Trt Week 6).

LAFA	
Single Ascending Dose, Fasted
 
Cohort 1: 4, 25, 60 mg + placebo (15 subjects)
 
Cohort 2: 2 and 10 mg + placebo (9 subjects)
 
Cohort 3: 4, 10, 25, 60 mg + Fentanyl (10 subjects)
	
No. of subjects with PK data available/total : 30/31
 
PK samples are collected at 0, 0.5, 1, 1.5, 2, 3, 4, 6, 8, 12, 24, 48, 72, and 96 h

LAFB	
Multiple Ascending Dose, Fasted
 
Cohort 4: 2 mg q.d. (9 subjects)
 
Cohort 5: 35 mg q.d. (9 subjects)
 
Cohort 6: 10 mg q.d. + ethanol (10 subjects)
	
No. of subjects with PK data available/total : 28/37
 
PK samples are collected at 0, 0.5, 1, 1.5, 2, 3, 4, 6, 8, 12, 24, 48, 72, 96.0, 120, 144, 168, 192, 216, 264 h

LAFC	
Receptor Occupancy (PET)
 
0.5 mg (1), 2 mg (4), 4 mg (2), 10 mg (4), 25 mg (1 subject)
	
No. of subjects with PK data available/total : 12/12
 
PK sample are collected at 0.5, 1.0, 2.5, 4, 6, 8, 12, 22.5 h

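### Biomarker group comparisons use change scores without baseline as a covariate, and time-point comparisons are not said to be paired, so precision is lost

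*Protocol*

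**What the plan says.** Protocol section 9.3 plans tabulation and summary statistics at each time point, then states: "Post-treatment changes in biomarker levels will be assessed by treatment group". The next sentence gives the method: "Analysis of variance (ANOVA) and t-test will be used to assess differences across groups and time points". The synopsis says the same. Neither place mentions a subject effect, pairing, a covariance structure or a baseline covariate, and neither says which sample is the baseline.

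The samples are repeated within subject. The blood-volume table in protocol section 8.1 has the row "Biomarker plasma 10 3 30": 10 mL, three samples, 30 mL in all. Serum biomarkers also have three samples. Section 8.9 leaves the timing to the schedule: "blood and saliva will be collected for the assessment of biomarkers at the time points indicated in the TES".

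The same protocol does more for its main endpoint. Section 9.2.1 specifies an MMRM for MADRS with "time-by-treatment interaction as factors and baseline total MADRS score as a continuous covariate", and section 9.2.2 applies the same model to SHAPS. The supplied SAP covers population PK and exposure-response only and has no biomarker analysis. Biomarkers are an exploratory objective in section 3 ("To explore mood-related biomarkers").

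**The concern.** ANOVA and t-test, named without qualification, do not settle two things that matter when each subject is measured repeatedly.

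- **Group comparison.** A change score removes baseline with a fixed coefficient of 1. Regression on baseline estimates the coefficient and leaves a smaller residual variance whenever the correlation is below 1. Leaving the covariate out discards information that has already been collected.
- **Comparison over time.** Day-to-day contrasts are within-subject. A two-sample t-test between time points would ignore the positive correlation, overstate the standard error and hide real change.

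What is at stake is sensitivity. Appendix 2 lists ten serum analytes, plasma ACTH and kynurenine metabolites, and salivary cortisol. Section 4.2 says that the effect on ACTH and cortisol after six weeks of treatment will be investigated. The trial is sized for MADRS, so any biomarker signal has to be found in whatever number of subjects that provides.

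**Working it through.** **The plan's own figure.** No sample size, power or significance level is stated for biomarkers. The only sizing, in section 9.1, rests on the "assumption of a treatment effect size of 0.45 in the mean change from baseline in MADRS total score", with 90% power at one-sided 0.20. It reproduces: n per arm = 2(0.8416 + 1.2816)²/0.45² = 9.016/0.2025 = 44.5, rounded up to 45. It is used below only as an illustrative arm size.

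**Inputs.** Three blood samples per subject (section 8.1). Outcome is change from baseline (section 9.3). The correlation r between baseline and follow-up is not in the documents, so r = 0.3, 0.5 and 0.7 are assumed, with equal variance at both times.

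**Group comparison at one visit.** With unit variance per measurement:
- change score: variance 2(1−r)
- baseline-adjusted (ANCOVA): variance 1−r²
- ratio: (1−r²)/[2(1−r)] = (1+r)/2
- difference: 2(1−r) − (1−r²) = (1−r)², which is positive for any r below 1

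| r | change | ANCOVA | ratio | variance reduction | SE reduction |
|---|---|---|---|---|---|
| 0.3 | 1.40 | 0.91 | 0.65 | 35% | 19% |
| 0.5 | 1.00 | 0.75 | 0.75 | 25% | 13% |
| 0.7 | 0.60 | 0.51 | 0.85 | 15% | 8% |

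The SE column is 1 − √ratio; at r = 0.5, 1 − √0.75 = 0.134.

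As an illustration, take 45 per arm, a standardized difference of 0.45 on the follow-up value and one-sided 0.20. Power is then 83.2%, 90.2% and 97.2% for the change score, against 91.9%, 94.8% and 98.4% for ANCOVA.

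**Comparison between two time points.** The true variance of the within-subject difference is 2(1−r); an unpaired test uses 2. The unpaired SE is therefore 1/√(1−r) times the correct one: 1.20, 1.41 and 1.83. A nominal two-sided 5% test would reject under the null in only 1.9%, 0.6% and 0.03% of trials.

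**Validity of the tests that fit the text.** In 4,000 simulated trials of 45 per arm, at nominal 5%:
- t-test on change at a single visit: 5.3%, 5.6% and 4.6%
- paired test between time points: 5.0%, 4.6% and 5.0%

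Both hold their level, so for the group comparison the loss is one of precision only.

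**How many on-treatment blood samples.** As the protocol schedule reads in the supplied text, biomarker blood is drawn at Visits 2, 5 and 9 (Days 1, 22 and 57), and the Day 22 sample is taken before dosing. SAP Table 1 places PK sampling "before and 2 hours after dosing on Day 22 (Day 1 Treatment Period"), so treatment starts on Day 22. On that reading Days 1 and 22 both precede randomized drug, and Day 57 is the only on-treatment blood sample. There are then two candidate baselines, and section 9.3 does not choose. The schedule table may be damaged in extraction, and its PK row does not match the SAP's PK days, so this should be checked against the original table.

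**The case against.** The strongest reply is that section 9.3 is brief rather than wrong. ANOVA can mean repeated-measures ANOVA, and a t-test can be paired. The SAP introduction itself uses the term for a mixed-model analysis with a group-by-time interaction in another study of this drug. The protocol also defers details to a Statistical Analysis Plan whose efficacy content is not in the supplied document, so pairing and covariates may be set elsewhere. The endpoints are exploratory, and section 9.3 allows further analyses.

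Much of this stands. It rules out three stronger readings that a reader might infer:
- **That baseline is ignored.** The sentence before the method assesses changes, which subtract baseline. What is missing is baseline as a covariate.
- **That the tests have inflated false-positive rates.** This would require several on-treatment values per subject to be pooled as if independent. The text does not say so, and the schedule as extracted leaves one on-treatment blood sample, so there would be nothing to pool.
- **That faulty results would carry into cross-study work.** Section 9.3 says that the biomarker data may be shared; standard errors and p-values do not travel with them.

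The precision point survives. Even if ANOVA means ordinary repeated-measures ANOVA with one pre-treatment and one on-treatment value, its group-by-time test is equivalent to the t-test on change, so the (1+r)/2 factor still applies.

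**Conclusion.** The point holds as a minor, free improvement. The group tests described are valid but less efficient than baseline-adjusted ones, with 35%, 25% or 15% of variance recoverable at r = 0.3, 0.5 or 0.7. That result rests on equal variances and on assumed correlations; r will differ by analyte. The time-point problem is conditional: only if the tests were run unpaired would the standard error be about 1.2 to 1.8 times too large, and the text does not say which is intended. No invalid error rate has been shown. The baseline sample for biomarkers is also undefined. The SAP's baseline definition covers MADRS, SHAPS and safety parameters, not biomarkers.

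**What to change.** State in section 9.3 or the biomarker analysis plan:

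1. Compare groups on each analyte by ANCOVA with treatment and the pre-treatment analyte value where there is one on-treatment sample. Where there is more than one, use an MMRM with treatment, visit, treatment-by-visit and baseline analyte value.
2. Test change over time by paired or within-subject contrasts.
3. Name the pre-treatment sample that serves as baseline.

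Log transformation can be left to each analyte's distribution. The cost is a few sentences and one model degree of freedom per analyte for the covariate. No new samples, visits or blood volume are needed.
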